7.8 STUDY ARTICLES

Control group:

- QuitGuide App [REDACTED]
- NRT with associated labeling (optional)

Intervention group:

- Pivot Breath Sensor
- USB charging Cable
- Replaceable Mouthpiece
- Quick Start Guide [REDACTED]
- Pivot App [REDACTED]
- Package Insert [REDACTED]
- Pivot Breath Sensor Educational Booklet [REDACTED]
- NRT with associated labeling (optional)

7.9 USER MANUAL AND TRAINING

Both Pivot and QuitGuide were designed with the intention that users are able to understand how to use these programs independently. For the Pivot Breath Sensor, a Quick Start Guide, Package Insert, Educational Booklet and package labeling are included with the device to aid the user and an online User Manual [REDACTED] is also available. All of these items will be accessible to study participants in the intervention arm; in addition, a phone number will be included within the labeling material to contact customer support. QuitGuide provides technical support to help users download and use the app through [contact].

7.10 STUDY ENVIRONMENT

The study will be performed remotely on an ambulatory basis. Participants will be emailed a link for their respective app to get started. For individuals in the intervention arm, the Pivot Breath Sensor will be mailed to the participant's indicated address and the participant will use the sensor at their discretion, going about life as they normally would.

7.11 STUDY PERSONNEL

The study team members will be trained by reading the study protocol. The study team members will have full training on the QuitGuide and Pivot apps, and operation of the Pivot Breath Sensor. Study team members will also have documentation of HIPAA / HITECH Security Awareness training and NIH Protecting Human Research Participants training.

7.12 IRB OVERSIGHT

This study will be conducted under IRB oversight.

8. STUDY PROCEDURE

8.1 SCREENING

See section 7.4 *Participant Recruitment and Informed Consent*

8.2 REGISTRATION

After electronically signing the Informed Consent Form, the participant will complete the online Baseline Questionnaire. After completing the Baseline Questionnaire, participants will undergo computer-generated randomization to either the intervention or control study group, as described in section 7.5 *Participant Randomization, Stratification and Enrollment*. Participants are then emailed a link for their assigned app. Upon opening the link, participants will register in their assigned app, providing baseline information on their smoking behavior. While participants are encouraged to select a quit date in their app that occurs within 30 days of enrollment, this is not required for participation.

8.3 ACTIVE PROGRAM USE

The participant will initiate use of their assigned program. To be considered enrolled, one must: sign the electronic informed consent form, complete the Baseline Questionnaire, and provide the date they first logged in to their assigned app. Participants may receive up to two text or email messages during the first week of the study reminding them to go into their study app and confirm they have done so. There is no pre-determined time limit on how long a participant can actively engage in their app, although it is expected most participants will complete engagement by 6 months from enrollment. For individuals enrolled in the intervention arm, coaching is available for up to 12 months from enrollment. In both arms, participants may order up to 12 weeks of NRT, in two-week increments over the first 12 months of the study. Pivot is designed to be a 12-month program. There is one possible biovalidation videocall visit at 12 weeks during this portion of the study and weekly online questionnaires at the end of weeks 1 through 12.

8.4 FOLLOW-UP

As it is expected that most participants will complete engagement in their respective programs by 6 months, the study will focus on follow-up at that point and beyond. The follow-up period includes three possible biovalidation videocall visits at 26, 52 and 104 weeks, and online questionnaires at 26, 52 and 104 weeks.

8.5 BIOVALIDATION

Biovalidation will be sought at 12, 26, 52 and 104 weeks in individuals who reported 7-day (or greater) PPA on the associated questionnaire (from 12, 26, 52 or 104 weeks). A videocall will be scheduled for within 7 days following the participant's response to the associated questionnaire. At the beginning of each biovalidation call, participants will be asked 7-day PPA status. Participants will be asked (yes/no) if they have smoked any other non-cigarette (ex. pipes, cigars, hookah) or combustible materials (ex. cloves, marijuana) over the last 24 hours. They will also be asked how many cigarettes they currently smoke per day. Participants who indicate they are not at least 7 days abstinent (i.e., answer "Yes" to the following question: "In the last 7 days have you smoked any cigarettes, even a single puff?") and/or indicate they currently smoke cigarettes will not be eligible to undergo further biovalidation testing during the visit. Participants who indicate they are at least 7 days abstinent and do not smoke cigarettes will be eligible to proceed with the testing. Participants who indicate they have smoked any other combustible materials over the previous 24 hours will be eligible to undergo biovalidation test, with the option to schedule a follow-up biovalidation test for the following day with instruction to not smoke the previously reported other combustible substance(s) over the intervening 24-hour period. If a participant is eligible for biovalidation and biovalidation is not achieved, the reason will be noted (ex. did not complete a biovalidation study visit, reported relapse so biovalidation visit was not completed, participant's breath CO sample was 10 ppm or more, etc.).

If this is the first study biovalidation visit a participant has participated in, the steps of the visit and the CO breath sample will be described in detail, with questions fielded and verbal confirmation the participant would like to proceed obtained before doing the biovalidation test. If this is not the first study biovalidation visit a participant has participated in, there will be a high-level review of the steps of the visit and the CO

breath sample, with questions fielded and verbal confirmation that the participant would like to proceed obtained.

Biovalidation will be obtained through CO breath sampling. For the 12-, 26- and 52-week biovalidation visits, participants in the intervention arm will use their Pivot Breath Sensor for this test. Participants in the control arm will be mailed a Pivot Breath Sensor prior to the visit that has a limited number (10 or less) of samples it can perform. For the 104-week biovalidation visit, all eligible participants who schedule the biovalidation visit will be mailed a Pivot Breath Sensor. On the call, participants will have the process of giving a breath sample described to them. They will be offered the chance to ask questions, and then study staff will provide an overview of the steps to give a breath sample. When they feel ready, they will give a breath sample and hold the breath sensor up to the screen immediately after completing the sample so that study staff on the videocall can see the CO ppm measurement on the breath sensor screen. A CO ppm value of less than 10 will be considered consistent with abstinence.[16]

After their first biovalidation visit, participants in the control arm will be instructed to not use the breath sensor beyond the visit, and to place the sensor in a safe place (for example, in the original packaging, in a closet) for use at a future biovalidation visit, should there be one. For future biovalidation visits, participants will use their existing breath sensor or will be sent a new one (fully functioning breath sensors for the intervention arm and sensors limited to 10 breath samples for the control arm for 12-, 26- and 52-week visits; and fully functioning sensors for all eligible participants for the 104-week visit) as needed. Participants will keep the breath sensor. While the sponsor will not request the sensors be mailed back, participants may mail their sensor(s) back to the sponsor if they prefer.

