7.3 STUDY OUTCOMES

- User engagement and retention in the program (number of app opens, number of days with at least one app open, number of weeks with at least one app open)
- Attitudes towards quitting: desire to quit, confidence to quit, difficulty to quit and self-efficacy
- Smoking behavior: quit attempts, change in cigarettes per day (CPD), smoking cessation via 7-and 30-day PPA (self-report and biochemically confirmed), continuous abstinence (self-report and biochemically confirmed), abstinence from all tobacco products, use of NRT
- Participant feedback on the set-up, use experience, design and impact of their assigned smoking cessation program

Outcomes include:

Primary:

- Total app opens in Pivot vs QuitGuide at 12 weeks (3 months)

Secondary:

- Change in expected difficulty in staying quit (participant self-report, scale 1-10) at 2, 4, 8, 12 weeks after enrollment
- Change in confidence levels towards quitting smoking (expected success in quitting, participant self-report, scale 1-10) at 2, 4, 8, 12 weeks after enrollment
- Desire to quit (yes/no) at 4 weeks after enrollment
- Self-reported abstinence (7-day and 30-day PPA) at 6, 8, 12, 26, 52 and 104 weeks after enrollment
- Self-reported abstinence (7-day PPA) at 2 and 4 weeks after enrollment
- Self-reported abstinence from all tobacco products at 6, 8, 12, 26, 52, and 104 weeks after

enrollment

- Biochemically confirmed abstinence at 12, 26, 52, and 104 weeks
 - To be considered biochemically abstinent:
 - Breath CO sample should be less than 10 ppm [16]
- Self-reported continuous abstinence at 26, 52 and 104 weeks, defined as a self-report of smoking no more than five cigarettes from 12 weeks after enrollment
 - 12 weeks is chosen because it allows for a full course of NRT, and it has been standard in studies that include pharmacotherapy for smoking cessation [17]
- Biochemically confirmed continuous abstinence at 26, 52, and 104 weeks, defined as a self-report of smoking no more than five cigarettes from 12 weeks after enrollment, and confirmation on all previous and present biovalidation tests:
 - Breath CO sample should be less than 10 ppm for participant to be considered abstinent [16]
- The proportion of participants who reduced their cigarettes per day (CPD) by $\geq 50\%$ compared to baseline at 4, 12, 26, 52 and 104 weeks

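### Confirmed continuous abstinence permits up to five cigarettes after week 12, but any puff in the 7 days before a visit rules out the CO test needed for confirmation

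*Combined protocol and SAP*

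**What the plan says.** Section 7.3 lists self-reported continuous abstinence at weeks 26, 52 and 104, "defined as a self-report of smoking no more than five cigarettes from 12 weeks after enrollment". The next outcome is "Biochemically confirmed continuous abstinence at 26, 52, and 104 weeks". It uses the same self-report allowance and adds "confirmation on all previous and present biovalidation tests", with CO below 10 ppm as the criterion.

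Section 8.5 sets out who is tested. Biovalidation is sought at weeks 12, 26, 52 and 104 "in individuals who reported 7-day (or greater) PPA on the associated questionnaire". On timing: "A videocall will be scheduled for within 7 days following the participant's response to the associated questionnaire". The call opens with the question "In the last 7 days have you smoked any cigarettes, even a single puff". Anyone who answers yes, or who says they currently smoke cigarettes, "will not be eligible to undergo further biovalidation testing during the visit". A person who smoked some other combustible material in the previous 24 hours may still be tested, "with the option to schedule a follow-up biovalidation test for the following day". No repeat test is described for a cigarette lapse. If an eligible participant is not validated, the reason is recorded.

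Neither Section 7.3, Section 8.5 nor Section 11.2 (Analysis) says how a visit without a test counts in the confirmed continuous endpoint.

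**The concern.** The outcome definition and the testing rule treat the same person differently. Someone who smokes one cigarette a few days before week 26, and none otherwise since week 12, meets the self-report part of the definition but cannot take the test that the confirmed version requires. They are unconfirmed because of when the lapse fell, not because of a CO result.

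The self-reported and confirmed versions stand side by side in Section 7.3, so the difference between them will be looked at. Part of it will come from the eligibility rule and part from CO readings of 10 ppm or more, and the endpoint itself does not separate the two.

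The requirement for confirmation on earlier tests raises a second question. If a visit without a test counts as an earlier test not confirmed, one lapse near week 26 would also decide weeks 52 and 104.

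**Working it through.** **Side-by-side reading**

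| Participant | Self-reported continuous abstinence (7.3) | Access to the CO test (8.5) | Confirmed version |
|---|---|---|---|
| One cigarette since week 12, mid-interval | Met | Yes | Decided by CO |
| One cigarette since week 12, within 7 days before the week-26 questionnaire or call | Met | No | Not confirmed at week 26, whatever the CO |
| Last cigarette within 7 days before the week-12 questionnaire, none since | Met, with zero cigarettes counted | Not offered at week 12; offered at week 26 | Depends on how the untested week-12 visit counts |

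Row 2 follows from the text alone. Row 3 arises because counting starts at week 12, while the week-12 test looks back 7 days before that.

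**Two readings of the earlier-tests requirement**

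- All scheduled tests: a blocked week-26 test removes the person at weeks 26, 52 and 104, and the person in row 3 is never confirmed.
- Tests actually taken: the loss is limited to the blocked visit, and the person in row 3 can be confirmed from week 26. The cost is that someone with no earlier tests can be called continuously confirmed on a single sample.

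**Scale, for illustration only.** The plan gives no lapse rate, so there is no figure of its own to reproduce. Assume k cigarettes fall on independent, uniformly random days over a period of D days, with a look-back of w days at its end:

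P(test blocked) = 1 − (1 − w/D)^k

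Periods from week 12: to week 26, 14 × 7 = 98 days; to week 52, 40 × 7 = 280 days; to week 104, 92 × 7 = 644 days.

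If the call is on the day of the questionnaire, w = 7. If it is 7 days later, the two look-backs together cover w = 14 days, but the period then also runs 7 days longer, so D = 98 + 7 = 105 for week 26.

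| Visit | w / D | k = 1 | k = 3 | k = 5 |
|---|---|---|---|---|
| Week 26, call same day | 7/98 | 7.1% | 19.9% | 31.0% |
| Week 26, call 7 days later | 14/105 | 13.3% | 34.9% | 51.1% |
| Week 52, call same day | 7/280 | – | – | 11.9% |
| Week 104, call same day | 7/644 | – | – | 5.3% |

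For example, 1 − (1 − 7/98)^5 = 1 − 0.690 = 0.310.

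Independence matters. If all five cigarettes fall on one day, the week-26 figure with w = 7 drops from 31% to 7/98 = 7%.

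**The case against.** The strongest reply is that the confirmed outcome is a conjunction of self-report and test confirmation, so it is meant to be stricter than self-report, and the plan reports self-report separately. That is fair, and it would be too much to say that the confirmed endpoint fails to measure its own definition. But the definition carries the five-cigarette allowance into the confirmed version, and the testing rule withdraws it for lapses near a visit. That conflict remains.

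A reader might infer that one lapse excludes a person for good, or that someone who stops in the week before week 12 can never be confirmed. The documents do not support either as a firm statement. The bar in Section 8.5 is worded for one visit, and a test that was never done is not plainly a previous test. The week-12 case has a further escape: Section 8.6 provides for questionnaire reminders, and a later answer moves the look-back.

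A reader might also divide 14 days by 98 and obtain 14%, 37% and 54% for 1, 3 and 5 cigarettes. That is inconsistent, because only 7 of those 14 days lie inside the 98-day period; the matching denominator is 105.

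Finally, it is tempting to say that the gap between the two versions will be taken for misreporting. The data can largely prevent this. Section 8.5 records reasons for eligible participants, with a reported relapse distinct from a high CO, and those stopped at the questionnaire can be found from their own 7-day answer. What is missing is a plan to tabulate them.

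**Conclusion.** The conflict is real but narrow. As written, a permitted lapse in the 7 days before a questionnaire or call leaves a person unconfirmed at that visit without any CO measurement. Loss at later visits, and loss of those who stopped in the 7 days before the week-12 assessment, are conditional: both require an untested visit to count as a failed earlier test, which the plan leaves open.

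The calculated probabilities apply only to participants with one to five cigarettes since week 12, and the documents do not give the size of that group. They also assume independent random lapse days; week 26 is the worst visit. They show that the effect need not be trivial for such a person, not how far the trial's confirmed rate would move.

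The primary outcome (app opens) and the sample size are untouched. This is a worthwhile clarification of one secondary endpoint.

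**What to change.** Reconcile Sections 7.3 and 8.5:

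1. At weeks 26, 52 and 104, offer the CO test to participants who report 7-day abstinence and also to those who report no more than five cigarettes since week 12, with CO below 10 ppm deciding confirmation. Keep the 7-day condition for confirmed 7-day abstinence. The week-12 test can stay as it is.
2. State before analysis how an untested visit counts among the previous tests. Cover explicitly the week-12 visit that was not offered because the person was still smoking shortly before the counting period began.
3. If the visits are already done, report the endpoint under both readings. In a table, separate those unconfirmed because they did not qualify for the test from those with CO of 10 ppm or more.

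The cost is protocol wording, a few extra 50-dollar calls with sensors mailed where needed, and a matching change to Section 7.6, which ties the paid visit to reported 7-day abstinence. Step 3 needs no new data collection.

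### At a control participant's first CO test (week 12, or a first visit at week 26 or 52) the sensor must be mailed, while Pivot participants already hold one; this can tilt confirmed abstinence toward Pivot

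*Combined protocol and SAP*

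**What the plan says.** **Who is tested and when (section 8.5).** Testing is sought at 12, 26, 52 and 104 weeks "in individuals who reported 7-day (or greater) PPA on the associated questionnaire". Timing is the same in both arms: "A videocall will be scheduled for within 7 days following the participant's response to the associated questionnaire". On the call 7-day abstinence is asked again, and anyone who has smoked a cigarette in that period is not tested.

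**Sensor supply at weeks 12, 26 and 52 (section 8.5).** In the Pivot arm, "participants in the intervention arm will use their Pivot Breath Sensor for this test". That device came with the programme; under section 7.10, "the Pivot Breath Sensor will be mailed to the participant's indicated address". For the other arm, "Participants in the control arm will be mailed a Pivot Breath Sensor prior to the visit", with a cap of 10 or fewer samples. After a first visit, control participants store the sensor for later visits, and either arm gets a new one only if needed.

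**Sensor supply at week 104 (section 8.5).** Both arms are treated alike: "all eligible participants who schedule the biovalidation visit will be mailed a Pivot Breath Sensor".

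**Outcome definitions (section 7.3).** Confirmed abstinence needs a breath CO below 10 ppm. Confirmed continuous abstinence needs "confirmation on all previous and present biovalidation tests".

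**Missing tests.** Section 8.5 records the reason when confirmation is not achieved. Section 11.2 gives no rule for analysing a missing CO test.

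**The concern.** Everyone who enters the testing window has just reported being abstinent. From then on, delay can take people out of the tested group, through relapse, a missed call or loss of contact, but it cannot bring anyone in. If one arm waits longer, that arm loses more people from the confirmed group even when smoking behaviour is identical.

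The longer wait is likely to fall on control participants at a first visit. Their eligibility is normally known only from the questionnaire response, and a device then has to reach them. A Pivot participant needs nothing posted.

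Confirmed abstinence and its continuous version are the trial's only biochemically verified smoking outcomes. A Pivot advantage on them could not be separated from easier access to the test.

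**Working it through.** **1. Is there a figure in the plan to reproduce?** Not for this outcome: the documents give no power, rate or test-completion figure for confirmed abstinence. The only sample-size figure concerns app opens (section 7.7): a difference of 10, SDs 25 and 19, power 0.8, alpha 0.05. With common SD √[(25² + 19²)/2] = 22.2, the noncentral-t calculation gives 156.72 in total, matching the stated 156.7. The present point does not depend on it.

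**2. Where the asymmetry applies.**

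| Visit | Pivot | Control, no earlier visit | Control, earlier visit |
|---|---|---|---|
| Week 12 | holds sensor | must be mailed one | none (this is the first visit) |
| Weeks 26, 52 | holds sensor | must be mailed one | reuses stored sensor unless a replacement is needed |
| Week 104 | mailed | mailed | mailed |

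**3. Effect on the confirmed rate.** Confirmed rate = (share self-reporting 7-day abstinence) × (share of those who complete the CO test). This assumes that an untested participant counts as not confirmed and that every completed test is below 10 ppm.

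Inputs:
- Self-reported abstinence of 32% in both arms, from the earlier Pivot cohort at end of programme (102/319, Background section).
- 90 per arm (section 7.7).
- Completion rates, which are assumptions: Pivot 90%, control varied.
- Chance of a significant result favouring Pivot, by exact enumeration of two binomials with a pooled two-sided z-test at 0.05. Section 11.2 does not state sidedness, so two-sided is assumed.

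| Control completion | Pivot confirmed | Control confirmed | Gap | Chance of significance favouring Pivot |
|---|---|---|---|---|
| 90% | 0.32 × 0.90 = 28.8% | 28.8% | 0 | 2.5% |
| 80% | 28.8% | 0.32 × 0.80 = 25.6% | 3.2 points | 7.0% |
| 70% | 28.8% | 0.32 × 0.70 = 22.4% | 6.4 points | 16.3% |
| 60% | 28.8% | 0.32 × 0.60 = 19.2% | 9.6 points | 32.4% |

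Each 10-point shortfall therefore costs 0.32 × 0.10 = 3.2 points, or 0.30 × 0.10 = 3.0 points at 30% abstinence. In people, 0.32 × 90 × 0.10 = 2.9, so about three untested control participants produce the 3.2-point gap. At 20% and 37.5% self-reported abstinence, the 90% versus 70% case gives about 11% and 19% in the last column.

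**4. Dilution at weeks 26 and 52.** Suppose a share s of control self-reporters already hold a sensor and complete at 90%, and first-time testers complete at 70%.
- s = 0.5: completion 0.5 × 0.90 + 0.5 × 0.70 = 80%; gap 0.32 × 0.10 = 3.2 points; chance 7.0%.
- s = 0.8: completion 0.8 × 0.90 + 0.2 × 0.70 = 86%; gap 0.32 × 0.04 = 1.3 points; chance 3.8%.

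**The case against.** **Sensor reuse.** A reader might infer that every control participant waits for the post at all three visits. Section 8.5 does not support that, since a control participant tested at week 12 stores the device for later. This part of the objection stands and limits the point to first visits and replacements.

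**Posting date.** A reader might take mailing inside the 7-day window as stated fact. The text says only that mailing precedes the visit. Abstinence is also asked at weeks 2, 4, 6 and 8, so earlier posting is possible, and the schedule of activities (section 8.8) is redacted. Mailing inside the window remains the natural inference, because eligibility depends on the questionnaire response, but it is an inference.

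**Late tests.** No consequence is given for a call after day 7, so it cannot be said that a late control test is void. Within the stated window the extra lag is a few days at most.

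**Carry-forward.** A reader might conclude that a missed week-12 test rules out confirmed continuous abstinence later. That is one reading of section 7.3. A visit never held may not count as a test.

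**Safeguards.** Completed visits earn $50 in both arms (section 7.6), videocall capability is checked before randomization (section 7.4), staff explain the test on the call, and reasons for non-confirmation are recorded (section 8.5). Self-reported abstinence is a separate outcome and could expose an arm difference confined to confirmation. These may limit or reveal the problem, but they do not equalise access, and no report of testing by arm is planned.

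**Importance.** This is a pilot powered on app opens, which are unaffected. That also stands.

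**Conclusion.** The point holds in limited form. Access to the CO test is unequal at week 12, and at weeks 26 and 52 for control participants without an earlier visit or needing a replacement. Any resulting loss of tests would lower confirmed abstinence in control and so favour Pivot.

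The direction rests on two assumptions: that control sensors are normally posted after the questionnaire response, and that untested participants are counted as not confirmed. The second follows from the definition, although section 11.2 does not state it for the analysis.

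The size is unknown. The figures of about 3 points per 10-point shortfall, and 7% or 16% false-positive chances for 10- and 20-point shortfalls at 32% abstinence, come from assumed completion rates. They do not show that a bias of that size will occur or that a Pivot advantage would be spurious. The matter concerns secondary outcomes and is worth correcting because the remedy is cheap.

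**What to change.** In section 8.5, use one sensor-supply and booking rule for both arms at weeks 12, 26 and 52. Either option would do:

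- **Extend the week-104 rule.** Mail a sensor to all eligible participants who schedule the visit, and have both arms test on the mailed device. Cost: about 0.30 × 90 = 27 extra sensors per visit for the Pivot arm if 30% are eligible. The sponsor supplies the device.
- **Set a common call window** that opens only after a mailed sensor could have arrived, and book no Pivot call earlier. The documents give no mailing time, so the sponsor must set the bounds, and the present 7-day limit may need rewording. Cost: procedure text and a slightly later Pivot call.

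Under either option the later call means slightly more relapse before testing in the Pivot arm. That is the price of comparability.

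Also state when control sensors are posted, how a late sensor and a missing CO test are handled, and whether a missed visit counts among the previous tests for continuous abstinence.

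Report by arm the numbers eligible, tested and relapsed before the call, and the days from questionnaire to call. Much of this can be drawn from the reasons already recorded. CO results among those tested may be shown, but only descriptively: that analysis conditions on attendance, the step that may differ by arm, and so cannot remove the bias.
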